1.2 STUDY OBJECTIVES

1.2.1 Primary Objective

1. Demonstrate the safety of a low-dose intravenous infusion of unfractionated heparin (LDIVH) in aSAH patients treated with coil embolization.
2. Demonstrate a positive clinical effect of LDIVH in aSAH patients through measurement of significantly better mean Montreal Cognitive Assessment (MoCA) scores in the LDIVH treated subjects at a 90-day follow-up visit compared to control patients.

1.2.2 Secondary Objectives

1. Measure the correlation between blood / CSF levels of inflammatory biomarkers (e.g. hsCRP, IL-6) and cognitive function (MoCA).
2. Demonstrate a reduction in blood / CSF levels of inflammatory biomarkers (e.g. hsCRP, IL-6) in the LDIVH treated subjects compared to controls.
3. Demonstrate a reduction in cerebral vasospasm in the LDIVH treated subjects compared to controls by measuring the proportion of patients in each group who:
 - i. Demonstrate moderately severe or severe angiographic vasospasm by CTA or DSA obtained within the prime vasospasm window
 - ii. Demonstrate moderately severe or severe vasospasm on transcranial Dopplers (TCDs)
 - iii. Demonstrate vasospasm related CT infarctions
4. Demonstrate a reduction in “Delayed Cerebral Ischemia” as defined by the Neurocritical Care Society:
 - i. Symptoms of neurological deterioration (e.g., hemiparesis, aphasia, altered consciousness) presumed to be related to ischemia
 - ii. Symptoms persist for more than one hour
 - iii. Symptoms cannot be explained by other physiological abnormalities
5. Demonstrate a reduction in the need for “rescue therapy” for delayed cerebral ischemia and / or symptomatic cerebral vasospasm
6. Demonstrate a difference between the LDIVH treated subjects and controls in the proportion of patients in each group who:
 - i. Have any fever (Temperature $\geq 38.3^{\circ}\text{C}$ / 101.0°F)
 - ii. Have multiple fevers (≥ 3 fever episodes)
7. Demonstrate a significant difference in “fever burden” between LDIVH treated subjects and control subjects
8. Demonstrate a difference between LDIVH treated subjects and controls in mean Daily Fever Burden during the LDIVH infusion.

9. Demonstrate better clinical outcomes in the LDIVH treated subjects compared to controls with one of the following measures:
 - i. mRS at 90 days and 1-year (Ordinal Regression Analysis)
 - ii. Barthel Index at 90 days
 - iii. Center for Epidemiologic Studies Depression Scale (CES-D) at 90 days and 1-year
 - iv. QOLIBRI-OS at 90 days and 1-year
 - v. Lawton IADLs at 90 days
 - vi. Trail Making Test Parts A&B at 90 days
 - vii. Return to Work Status at 90 days and 1-year
 - viii. MoCA at 1-year
10. Perform Pre-specified Subgroup Analysis of Outcome measures for LDVIH and Control groups using the following subgroup designations:
 - i. Sex (Male versus Female)
 - ii. Admission CT Hijdra Sum Score (<23 versus ≥ 23)
 - iii. Aneurysm location (ACoA Aneurysm location vs. all others; any location; anterior circulation versus posterior circulation)
 - iv. Infection requiring Antibiotic Treatment versus no infection
 - v. Elevated hsCRP at enrollment vs. normal levels at enrollment
 - vi. WFNS 1 vs. 2
 - vii. Modified Fisher grade 3 and 4 while excluding accidental enrollments with Modified Fisher not equal to 3 or 4
 - viii. Chemical DVT prophylaxis: UFH 5000 units twice daily, or increased dose in obese patients according to SOC
 - ix. LDVIH arm: LDIVH infusion >10 days vs. ≤ 10 days
 - x. LDIVH arm: Initiation of LDIVH within 48 hours of hemorrhage ictus vs. > 48 hours
 - xi. LDIVH arm: Anti-Xa (Infusion Day 6) value < 0.20 IU/mL vs. ≥ 0.20 IU/mL
 - xii. Vasospasm related CT infarction vs. No vasospasm related CT infarction
 - xiii. Tobacco smoking versus no tobacco smoking

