Peak and Overall Plasma and CSF levels of hsCRP at enrollment and, infusion days #2, 4, 6, and 10 compared between groups.

-SECONDARY CLINICAL EFFECT ENDPOINTS

Trail Making Test Parts A&B at 90 (± 10) days post enrollment.

MoCA at 1-year (± 30 days)

Center for Epidemiologic Studies Depression Scale (CES-D) at 90 (± 10) days post enrollment

Return to work status between groups at 90 (± 10) days

SECONDARY EXPLORATORY PRESPECIFIED BIOMARKER OUTCOMES

Plasma and CSF levels of IL-6, TNF- α , P-Selectin, sICAM-1, HMGB-1, MRP8/14 plasma levels at enrollment and infusion day #2, 4, 6, and 10

ADDITIONAL PRE-SPECIFIED

Rate of MoCA ≤ 20 between groups at the 90-day follow-up visit.

**EXPLORATORY
OUTCOME ANALYSES**

In-hospital incidence of any fever ($> 38.3^{\circ} \text{C}$; $\geq 101.0^{\circ} \text{F}$), Incidence of multiple fever episodes (≥ 3), and Mean Daily Fever Burden.

GCS and NIHSS at enrollment and infusion days # 2,4,6,10, discharge and 90 (± 10) days

MoCA at post-enrollment day #1, 6 and 10

Correlation analysis between MoCA scores and inflammatory biomarker levels with and without adjusting for hemorrhage burden (Hijdra Sum Score).

Incidence of moderate and severe Radiographic Cerebral Vasospasm based on a CTA, MRA, or Catheter DSA obtained between PBD # 6-12 as determined by an independent and blinded core imaging lab.

Incidence of TCD criteria for significant vasospasm (velocities $>200 \text{ cm/s}$ and / or MCA / ICA (Lindgaard) ratio >6)

Incidence of TCD criteria for absence of vasospasm (velocities $<120 \text{ cm/s}$)

Incidence of clinical vasospasm requiring rescue therapy (eg, pressors, endovascular treatment)

Incidence of "Delayed Cerebral Ischemia" defined as:

- Symptoms of neurological deterioration (e.g. hemiparesis, aphasia, decreased level of consciousness)
- Symptoms last for more than an hour
- Symptoms are not explained by other physiological processes (e.g., hydrocephalus, hypotension)

CT or MRI evidence of Vasospasm Related Cerebral Infarction on post-infusion (discharge) imaging as scored by an independent and blinded core imaging lab

Global outcome as measured between group ordinal regression analysis of the modified Rankin Scale score at 90-days and 1-year.
Return to work status between groups at 1-year.
Lawton IADLs at 90 (± 10) days
QOLIBRI-OS at 90 (± 10) days and 1-year.
Checklist Individual Strength-subscale Fatigue (CIS-f) at 90 (± 10) days
Barthel Index at 90 (± 10) days and 1-year

**INVESTIGATIONAL

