10.4 General Statistical Plan

Patients enrolled will be presented. On-study protocol violations will also be presented. Patients who do not complete the required observations will be listed and evaluated separately as necessary. Reasons for study discontinuation and date of withdrawal from study will be presented.

Descriptive statistics related to the participant characteristics, treatment, and prognostic factors will be reported. For the continuous variables mean (95% confidence interval), median (minimum and maximum) will be reported and for discrete variables frequency and percentages will be reported. For continuous variables a two sample t-test/rank sum test will be used to compare between groups. A Chi-square test will be used for establishing association between categorical variables. For example MoCA will be compared between two groups using a contrast based t test in addition to simple two sample test either based on a linear regression or Mixed model approach when multiple observations on sample subject is considered. A discrete outcome such as prevalence of 'have any fever' between treatment and control arms will be tested using a logistic regression analyses. In order to examine the significant prognostic factors, we will use the multiple linear and logistic regression models in multi-variable setting.

A significance level of 5% will be used to declare results significant. For selected primary outcome variables we will report adjusted p-values for multiplicity in addition to unadjusted p-values. All calculations will be performed with methods described in Walker et al. (2010), Rosner (2010) and with SAS statistical software (SAS, 2003).

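### Secondary objective 9 can be met by any one of eight clinical measures (12 or 13 tests) at an unadjusted 5%, and the synopsis classes seven of the 13 tests as exploratory

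*Protocol*

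**What the plan says.** Objective 9 in protocol section 1.2.2 reads "Demonstrate better clinical outcomes in the LDIVH treated subjects compared to controls with one of the following measures" and lists eight measures: mRS, Barthel Index, CES-D, QOLIBRI-OS, Lawton IADL, Trail Making A and B, return to work, and MoCA at one year. Four of them are taken at two time points. The depression entry, for example, is "Center for Epidemiologic Studies Depression Scale (CES-D) at 90 days and 1-year".

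Section 10.4 sets a 5% level for declaring results significant and does not say whether it is one- or two-sided. On multiplicity it says "For selected primary outcome variables we will report adjusted p-values for multiplicity in addition to unadjusted p-values". Section 10.1 adopts one-sided procedures, but in its discussion of MoCA.

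The synopsis (section 1.1) ranks the outcomes itself. Its secondary clinical effect endpoints are Trail Making A and B at 90 days, MoCA at one year, CES-D at 90 days and return to work at 90 days. Its exploratory list contains "Global outcome as measured between group ordinal regression analysis of the modified Rankin Scale score at 90-days and 1-year", together with Barthel, QOLIBRI-OS, Lawton and one-year return to work. Vasospasm, delayed cerebral ischemia, rescue therapy and fever are on that exploratory list too, whereas section 1.2.2 makes them objectives 3 to 8, each worded as an effect to be demonstrated.

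The synopsis entry on study success requires better 90-day MoCA or lower inflammatory biomarkers, with no significant bleeding difference attributable to treatment. Objective 9 plays no part in it.

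**The concern.** An objective that is met when any one of many tests succeeds has an error rate well above that of each test. Here the disjunctive wording, the 5% level and the restriction of adjustment to primary outcomes are all written into the protocol. Read together, they let a single chance finding among 12 or 13 stand as a demonstrated clinical benefit.

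The labels add to this. An investigator could report mRS or vasospasm as a secondary objective that was met, citing section 1.2.2, while the synopsis calls the same analysis exploratory. The trial is meant to inform whether a Phase III study is warranted, and a claim of better clinical outcomes would naturally be read in that light.

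**Working it through.** **1. The plan's own figures.** The protocol states no error rate for objective 9. Its nearest figure is Table S1 in section 10.1, for 90-day MoCA. A one-sided 5% Welch test with SDs 7.0 and 2.5 and a difference of 3 reproduces the 40, 46 and 54 per arm exactly (power 80.8% at 40). So the one-sided 5% is confirmed for 90-day MoCA; nothing extends it to objective 9 or rules it out there.

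**2. Counting the tests and setting the labels side by side.**

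| Measure in objective 9 | Tests | Synopsis status |
|---|---|---|
| mRS, 90 days and 1 year | 2 | exploratory |
| Barthel, 90 days | 1 | exploratory |
| QOLIBRI-OS, 90 days and 1 year | 2 | exploratory |
| Lawton IADL, 90 days | 1 | exploratory |
| Return to work, 1 year | 1 | exploratory |
| Return to work, 90 days | 1 | secondary |
| CES-D, 90 days | 1 | secondary |
| Trail Making A and B, 90 days | 2 | secondary |
| MoCA, 1 year | 1 | secondary |
| CES-D, 1 year | 1 | in neither list |

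The total is 7 exploratory + 5 secondary + 1 unplaced = 13, or 12 if Trail Making A and B are one test.

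**3. Chance of at least one false result favouring heparin.** Let each test have error a in heparin's favour: a = 0.025 for a two-sided 5% test counted only for benefit, or a = 0.05 for a one-sided 5% test. For k independent tests the chance is 1 − (1 − a)^k. For k test statistics with common correlation ρ it is

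1 − ∫ φ(u) · Φ[(c − √ρ·u)/√(1 − ρ)]^k du,

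with c = 1.960 or 1.645. The correlation is an assumption, because the protocol gives none.

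| k, test | ρ = 0 | ρ = 0.3 | ρ = 0.5 | ρ = 0.7 |
|---|---|---|---|---|
| 13, two-sided 5% | 28.0% | 21.4% | 16.7% | 12.0% |
| 13, one-sided 5% | 48.7% | 35.7% | 28.1% | 20.6% |
| 12, two-sided 5% | 26.2% | 20.2% | 16.0% | 11.6% |
| 12, one-sided 5% | 46.0% | 34.2% | 27.0% | 19.9% |
| 8, two-sided 5% | 18.3% | 15.2% | 12.5% | 9.5% |
| 8, one-sided 5% | 33.7% | 26.7% | 21.9% | 16.8% |

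The rows for 8 show a reading with one test per measure.

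**4. Size relative to nominal.** For 13 tests and ρ from 0.3 to 0.7, the two-sided ratios are 0.120/0.025 = 4.8 to 0.214/0.025 = 8.6. The one-sided ratios are 0.206/0.05 = 4.1 to 0.357/0.05 = 7.1. The inflation is therefore about 4 to 9 times.

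**5. Would relabelling alone be enough?** The five secondary tests, unadjusted and independent, still give 1 − 0.975^5 = 11.9% (two-sided 5%, benefit direction), so the smaller family also needs an adjustment.

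**The case against.** The strongest reply is that this is a list of objectives in a Phase II protocol and not a decision rule. Section 10 contains no formal test of objective 9, and multiplicity for secondary outcomes is commonly left to a statistical analysis plan, which is not at hand. Silence on that would indeed be no finding. The point does not rest on silence, though. The any-one criterion, the 5% level and the restriction of adjustment to selected primary outcomes are stated, and a statistical analysis plan that followed them would inherit all three. It could impose a stricter rule, but it would still face two protocol sections that rank the same outcomes differently.

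The second reply is that the consequence is limited, and that stands. A reader might infer that the trial could be declared a success on objective 9. The synopsis entry on study success does not support this, since it uses 90-day MoCA or biomarkers, with the bleeding condition.

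A reader might also infer that everything in section 1.2.2 beyond the four synopsis secondary clinical endpoints is exploratory in the synopsis. That is wrong for the biomarker objectives. Biomarker reduction (objective 2) is a synopsis secondary objective, hsCRP is the primary biomarker endpoint under the secondary endpoints, and biomarker reduction is one route to study success. The association between biomarkers and cognition (objective 1) is a synopsis secondary objective, although the correlation analysis also appears in the exploratory list.

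Finally, a reader might want to attach a false-positive rate to objective 10, "Perform Pre-specified Subgroup Analysis of Outcome measures for LDVIH and Control groups using the following subgroup designations". The protocol states no within-level test and no claim for these subgroups. Three designations lie within the heparin arm only, and one is a restriction of the population. Any such rate would rest on a construction that the documents do not contain.

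**Conclusion.** The concern holds as a matter of a secondary claim. As written, one favourable result among 12 or 13 tests meets objective 9, and seven of the 13 are exploratory elsewhere in the same protocol. With no true effect, the chance of at least one false favourable result among 13 is about 12–21% for two-sided 5% tests and 21–36% for one-sided 5% tests. These ranges assume equal correlations of 0.3 to 0.7. No single value within them can be quoted as the protocol's own, because it fixes neither the correlation nor the sidedness for these tests. Counting 12 tests hardly changes the result; counting 8 lowers it without removing the problem. The separate conflict of labels for objectives 3 to 8 needs no assumption, as it is visible on the page. This should be corrected, but it does not threaten the trial's definition of success.

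**What to change.** - In objective 9, delete the words that make any one measure sufficient.
- Restrict the secondary clinical claim to the synopsis secondary clinical endpoints: Trail Making A and B, one-year MoCA, 90-day CES-D and 90-day return to work. State the sidedness, and add a sentence to section 10.4 giving this family of five tests a multiplicity adjustment such as Holm (first step 0.05/5 = 0.01). Testing the family only after 90-day MoCA, or in a particular fixed order, would be a matter of preference.
- Label the remaining objective 9 measures and objectives 3 to 8 exploratory, as the synopsis does. Report them as estimates with confidence intervals and without the language of demonstration.
- Leave biomarker objectives 1 and 2 secondary.
- Assign one-year CES-D a status in the synopsis; if it becomes secondary, it joins the adjusted family.

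The cost is rewording section 1.2.2, one synopsis entry and a sentence in section 10.4. No patients or data are added. The downside is that fewer outcomes can be claimed as demonstrated.

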4. SELECTION AND ENROLLMENT OF SUBJECTS

4.1 INCLUSION CRITERIA

1. Patient age is between 18 to 70, inclusive
2. Historical modified Rankin Scale Score 0-1
3. Aneurysmal subarachnoid hemorrhage caused by a ruptured saccular aneurysm confirmed by catheter angiography that is repaired by endovascular coil embolization. Initiation of the coil embolization procedure should occur within 48 hours from the time of the aneurysm rupture (ictus). In patients where the exact time of the ictus is uncertain, a reasonable estimate of the time of ictus may be assigned. This reasonable time estimate should be considered likely accurate to within hours of the true unknown time.

4. Quality of aneurysm embolization is interpreted to be Raymond-Roy Score of 1 (Complete) or 2 (Residual Neck) indicating that the aneurysm is adequately secured. A tiny amount of contrast in the body of the aneurysm is acceptable as long as the physician considers the aneurysm secured and to NOT represent a Raymond-Roy Score of 3 (Residual Aneurysm). Please see diagram below:

5. WFNS grade 1 or 2 as assessed after repair of the aneurysm during screening but prior to randomization. A patient who presents with a WFNS greater than 2 who then improves with resuscitation, ventriculostomy, or time is acceptable.

- The modified GCS (mGCS) is the sum of the best eye-opening response, the best verbal response and the best motor response (best extremity). It is used to determine the WFNS according to the tables below:

Adult modified Glasgow Coma Scale (mGCS)

Test	Responses	Value
Eyes opening Response (1-4)	No Response	1
	to pain	2
	to voice	3
	opens eyes spontaneously	4
Verbal Response (1-5)	No Response	1
	Incomprehensive words	2
	Inappropriate words	3
	Disoriented	4
	Oriented	5
Motor Response (1-6)	No Response	1
	Abnormal extension (decerebrate posturing)	2
	Abnormal flexion (decorticate posturing)	3
	Withdrawal	4
	Localizes	5
	Follows Commands	6

World Federation of Neurological Surgery (WFNS) SAH Grading Scale

[figure not shown]
WFNS Grade	mGCS Score	Motor Deficit
1	15	Absent
2	14 - 13	Absent
3	14 - 13	Present
4	12 - 7	Present or Absent
5	6 - 3	Present or Absent

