6.18 Discharge From Acute Care Setting

The patient will be discharged from the acute care setting per the normal SOC. The study patient is not expected to require any additional days of hospitalization or days in the intensive care unit by being enrolled in this trial. However, if the patient experiences a complication directly related to study drug infusion, there may be an increased length of stay as a result. Increased costs attributed to this unlikely event will be the burden of the patient and/or clinical site. The study's investigators and the University of Louisville (or any of its subsidiaries including the University of Louisville Research Foundation) will not provide indemnification to the clinical sites or patients against any increased expenses related to complications attributed to any patient's participation in this study. This will be listed as one of the risks of enrollment on the patient's informed consent document.

When a patient is clinically ready for discharge, they will be discharged from the hospital. Completion of the study drug infusion through the end of post-enrollment day 14 will not be an absolute requirement if the patient could otherwise be discharged. However, in our experience, it is rare for a patient with modified fisher grades 3 to be ready for discharge prior to post-enrollment day # 14. The total duration of the study drug infusion will be recorded, and any decreased length of study drug infusion because of early discharge will be noted but will not be considered a study deviation.

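### Subgroups ix (infusion duration), x (time to start) and xi (day-6 anti-Xa) exist only in the LDIVH arm, so they cannot separate an effect of heparin timing, duration or exposure from prognosis

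*Protocol*

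**What the plan says.** Protocol section 1.2.2, item 10, announces: "Perform Pre-specified Subgroup Analysis of Outcome measures for LDVIH and Control groups using the following subgroup designations". Several entries, such as sex, aneurysm location and WFNS grade, carry no arm restriction. Three are restricted to the heparin arm:

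- ix: an infusion lasting more than 10 days, against 10 days or fewer
- x: "LDIVH arm: Initiation of LDIVH within 48 hours of hemorrhage ictus", against a later start
- xi: day-6 anti-Xa below 0.20 IU/mL against 0.20 IU/mL or more.

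Section 6.8 says controls receive no study infusion, so start time and duration have no control counterpart as written. Day-6 anti-Xa is also measured in controls (section 6.9), but they are on subcutaneous heparin and the entry does not use their values. Section 10.4 gives general regression language that is not tied to these subgroups. Nothing in the protocol labels the three entries as descriptive.

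**The concern.** Each entry splits heparin patients by something randomization did not assign. A difference between the two parts mixes any heparin effect with whatever put patients in one part or the other.

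For x, that is mainly how late the patient reached coiling. For ix, it is the patient's course after randomization. For xi, it is individual drug handling, rate adjustments and interruptions up to day 6.

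The trial is meant to inform a Phase III decision (section 1.1). Section 5.2 already argues that a later start may lose benefit and that up to 14 days offers the most opportunity to benefit. A difference caused only by prognosis could look like support for either view. For timing, a comparison that keeps the randomized control is available from times both arms already need for eligibility.

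**Working it through.** **1. What decides membership of x.** Coiling must begin within 48 h of ictus (section 4.1, item 3). Heparin starts 12 ± 4 h after coiling is completed (section 4.1, item 8; section 6.8). Assume a procedure of 1–3 h, which the protocol does not state.

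- Latest start: 48 + 3 + 16 = 67 h after ictus.
- A start after 48 h requires coiling to begin later than somewhere between 48 − 3 − 16 = 29 h and 48 − 1 − 8 = 39 h.

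Membership is therefore set mainly by presentation and coiling delay. Patients are randomized after coiling (section 6.4), so this delay is fixed beforehand in both arms.

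The size of the late group depends on an assumed distribution of coiling times. It is about 13 of 44 if uniform over 0–48 h, and about 2–4 of 44 if most patients are coiled early (exponential, mean 12–18 h).

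**2. What decides membership of ix.** Infusion can be shortened by:

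- bleeding (6.10.3), a suspected allergic reaction (6.10.2), suspected HIT (8.4, typically 5–10 days after exposure begins) or other safety stops (9.2), which tend to mark a worse course;
- early discharge (6.13, 6.18), which tends to mark a better one, although section 6.18 says "it is rare for a patient with modified fisher grades 3 to be ready for discharge" before day 14.

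Example with no drug effect. The 26.4 is the pilot LDIVH mean in section 10.1; the other inputs are assumed.

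- 6 complication stops at MoCA 22 and 2 early discharges at 28: short-group mean (6×22 + 2×28)/8 = 23.5. Apparent gain from longer infusion: 26.4 − 23.5 = 2.9 points.
- 2 stops and 8 discharges: (2×22 + 8×28)/10 = 26.8. Apparent gain: 26.4 − 26.8 = −0.4 points.

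The sign depends on the mix of reasons for stopping.

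**3. Planning inputs.** Section 10.1 gives 40 evaluable per arm, SD 7.0 (control) and 2.5 (LDIVH), difference 3, one-sided 5%. SE = √(49/40 + 6.25/40) = 1.175. The unequal-variance t test gives 80.8% power at 40 per arm, so Table S1 reproduces. This is context only: it fixes the size of the arm being split.

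**4. False positives for x.** Assume heparin timing has no effect, and that late patients score 1.5 or 2 points lower in both arms for other reasons. The test is a two-sided 5% Welch test within 40 LDIVH patients, SD 2.5.

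| Late of 40 | Gap 1.5 | Gap 2 |
|---|---|---|
| 2–4 | about 14–16% | about 18–23% |
| 6–12 | about 22–38% | about 35–59% |

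With only 2 late, the Welch test rejects in about 13% of trials even with no gap, so part of the first row is small-sample behaviour of the test. The arm-by-time interaction rejects in about 5%, because the common gap cancels between arms.

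**5. Precision of the interaction.** With L late per arm, SE = √[(2.5² + 7.0²)(1/L + 1/(40−L))], where 2.5² + 7.0² = 55.25. The difference detectable with 80% power (two-sided 5%) is about 2.80 × SE.

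| L | SE | Detectable interaction (MoCA points) |
|---|---|---|
| 12 | 2.57 | 7.2 |
| 6 | 3.29 | 9.2 |
| 4 | 3.92 | 11.0 |
| 2 | 5.39 | 15.1 |

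For a true 3-point interaction, power is about Φ(3/2.57 − 1.96) = 21% with 12 late and Φ(3/3.29 − 1.96) = 15% with 6 late.

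**The case against.** Item 10 names subgroups but no test, model or interpretation, and these details often sit in a statistical analysis plan, which is not at hand. The item's opening words could mean that each LDIVH subset is shown beside the controls. Study success (section 1.1) does not depend on any of the three entries. Eligibility is narrow (WFNS 1–2 after coiling, historical mRS 0–1, age up to 70), which may limit how far early and late patients differ. The unbiased alternative for timing is too imprecise to answer the question.

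Most of this stands and limits the point. It does not remove it: the restriction to one arm is in the protocol's own wording, and setting an LDIVH subset against all controls is still not a randomized contrast, because no matching control subset is defined.

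A reader might infer more than the protocol supports:

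- *That the results will be read as timing or duration effects.* The protocol states no interpretation. What can be said is that the contrasts cannot tell such effects from prognosis.
- *That the group with 10 days or fewer will be mainly patients with complications.* Infusion may resume after bleeding, after HIT is ruled out, after a reaction with another cause, and after procedures (6.10.3, 8.4, 6.10.2, 9.1). A complication therefore need not mean a short infusion.
- *That early stopping also biases x.* It does not. The problem for x is prognosis and delay to coiling.
- *That false-positive rates of 22–59% are to be expected.* They need 6–12 late patients and an assumed prognostic gap.

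**Conclusion.** The point holds in a limited form. Subgroups ix, x and xi are non-randomized comparisons within the heparin arm, and none can separate heparin timing, duration or exposure from prognosis. For ix the direction of bias cannot be predicted. This structural conclusion rests on the protocol's wording alone.

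The error rates do not. They rest on an assumed 1.5–2 point prognostic gap and an assumed late share, and would be lower with a smaller gap. With very few late starters, x is mainly uninformative whichever way it is analysed.

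These are secondary subgroup analyses, so severity is modest.

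**What to change.** Reword three entries in section 1.2.2, item 10.

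- **x:** define it in both arms by time from ictus to completion of coiling, preferably in continuous hours. Report the treatment-by-time interaction with its confidence interval, labelled exploratory. State that the estimate is imprecise: on the binary split, only interactions of about 7–9 MoCA points or more are detectable with 12 or 6 late per arm, and larger ones with fewer.
- **ix:** report infusion duration with the reason for stopping, as a description of exposure.
- **xi:** report day-6 anti-Xa in the same way.

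Label ix and xi as non-randomized and make no claim about an effect on outcome.

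The cost is a change of wording. Ictus and coiling times are already needed for eligibility in both arms, and section 9.2 already records reasons for early discontinuation. No treatment procedure changes. The price is a wide interval for the timing question, which the present contrast avoids only by accepting bias.
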